Deep brain stimulation (DBS) has become an evidence-based treatment for movement disorders such as Parkinson's disease. Recent animal studies of DBS suggest that neuronal subpopulations may be specifically activated by burst-type DBS and that this type of electrical stimulation programming may improve the efficacy and durability of DBS. Burst-type DBS is defined as a novel stimulation protocol in which intermittent bursts of traditional high-frequency rectangular wave stimulation are delivered. Implanted pulse generators (IPGs) have the capability to deliver such stimulation by setting specific "on" and "off" times, however there is no published human data on the results of such programming in patients undergoing DBS for movement disorders such as PD.

Primary Objective

The primary objective is to determine change in the UPDRS-III motor score in the medication OFF state with burst-type DBS programming in the acute setting (after 30 minutes) and then after 6 months and 12 months for patients with bilateral subthalamic nucleus DBS for Parkinson's disease.

Study Design:

Randomized, double-blind cross-over study with N= 5 patients implanted with bilateral subthalamic nucleus DBS.

Study Site:

Allegheny General Hospital
Neuroscience Institute
[name]
[name]

Study Population

Patients for this study (N= 5) should have bilateral STN-DBS (with Boston scientific Gevia or Genus technology) implanted for Parkinson's disease. The patients should be on stable DBS programming settings and stable medication regimens defined as no DBS programming changes or Parkinson's disease medication changes over past 2 weeks. The DBS implantation should have been performed by either [name], MD or [name], MD at Allegheny General Hospital and implantation surgery must have occurred a minimum of 6 months prior to the day of enrollment.

Recruitment Strategy

Subjects will be recruited from the DBS practice of investigator neurosurgeons [name] MD and [name] MD. Patients will be identified by the neurosurgeons as well as by DBS nurse [name] RN and physician assistant [name] PA-C.

Recruitment will stop when approximately 5 subjects are enrolled. It is expected that approximately 15 subjects will be enrolled to produce 5 evaluable subjects.

Subject Replacement

In the event that consented subjects are unable to complete study procedures for any reason (e.g. unable to attend visits, adverse reaction to burst programming, or other concerns determined by primary investigator), subjects will be withdrawn from the study and primary investigator may screen and enroll replacement subjects(s) to ensure the number of completed subjects equals 5.

Inclusion Criteria

1. Adult patients (male and female) ages 18-85
2. Bilateral DBS-STN (subthalamic nucleus) target for idiopathic Parkinson's disease implanted minimum 6 months prior to the day of study enrollment
3. Stable DBS programming settings and Parkinson's disease medications defined as no changes to either within past 2 weeks
4. Comfortable using DBS controller to turn off device prior to study visits
5. Able to provide informed consent and complete follow-up visits

Exclusion Criteria

1. DBS technology other than Boston scientific Genus/Gevia
2. Unable to complete follow-up visits
3. DBS brain targets other than STN (subthalamic nucleus)
4. Signs of progressive cognitive decline

Subject Completion/Withdrawal

Subjects may withdraw from the study at any time without prejudice to their care. They may also be discontinued from the study at the discretion of the Investigator for lack of adherence to study treatment or visit schedules, AEs, or due to medical illness which complicates follow-up. The Investigator or the Sponsor (if applicable) may also withdraw subjects who violate the study plan, or to protect the subject for reasons of safety or for administrative reasons. It will be documented whether or not each subject completes the clinical study. If the Investigator becomes aware of any serious, related adverse events after the subject completes or withdraws from the study, they will be recorded in the source documents and on the CRF.

The study duration per subject will be up to 365 days.

Description of Devices and Assessments

DBS System

Boston Scientific Neuromodulation (BSN) Vercise™ System: A neurostimulation device consisting of an implantable pulse generator (IPG), integrated rechargeable battery, two DBS leads, two DBS extensions, Burr Hole Cover, surgical tools, GUIDE XT Software and external devices (programming system, remote control, and charging system). The implanted pulse generator (IPG) for this study will be either the Gevia or Genus model.

UPDRS (United Parkinson's Disease Rating Scale)

The UPDRS is an assessment that can be utilized to follow the progression of PD and is completed by interviewing the patient. The UPDRS was developed in 1987 by neurologists as a gold standard to determine response to medications and has been heavily utilized to standardize the response to DBS. There are 4 sections of the test (I-IV), as follows:

- (I) Mentation, Behavior, and Mood;
- (II) Activities of Daily Living (ADL);
- (III) Motor Examination;
- (IV) Complications of Therapy.

This study will utilize only the Motor Examination (Section III) for study visits. Section III contains 14 items to evaluate overall motor disability, including the classic symptoms of PD. The questions in this section assess speech, facial expression, tremor at rest (for face, hands, and feet), action or postural tremor of hands, rigidity, finger taps, hand movements, rapid alternating movements of hands, leg agility, arising from chair, posture, gait, postural stability, and body bradykinesia and hypokinesia. Each item is scored on a scale from 0 (normal) to 4 (severe, marked, or unable), with the total possible score for the 14 items, including separate questions regarding symptoms present axially and in appendages, ranging from 0 to 108.

Summary of Study Visits

Screening

[figure not shown]
Patients will be approached for possible study participation during a routine, standard of care visit. All interested patients will undergo screening to determine eligibility into the study. Screening will include the following:

- Review and signing of informed consent document.
- Demographics: Date of birth, Gender, Ethnicity, Handedness
- Medical history: Surgical/Interventional Procedure History, Parkinson's Disease History (presence of symptoms required for eligibility will be documented), presence and in some cases severity of selected symptoms of either PD or PD medications that can also occur as a side effect of STN DBS dopamine dysregulation syndrome (DDS);
- Review of current Parkinson's disease medications: Dosage/frequency (Start Date, Stop Date)
- Review of concomitant medications

Visit One- Baseline (\leq 30 Days after Screening)

- Parkinson's disease dopaminergic medications will be withdrawn overnight to establish medication-OFF state and DBS will be turned OFF overnight for establishing DBS-OFF state. Examiner will establish a UPDRS-III baseline with medication-OFF, DBS-OFF state.
- Unblinded examiner will then turn the DBS ON to the patient's baseline DBS settings continuously ON or to burst DBS mode (baseline DBS settings for the patient with DBS set to 1 sec ON, 4 sec OFF), based on results of randomization. The patient will be blinded to this programming change and will be kept at this initial setting for 30 minutes.
- Next, a blinded examiner who did not perform the programming change will perform a UPDRS-III evaluation. Next, the DBS will be turned off for 15 minutes to permit for a washout period.
- Next, the DBS will be turned on by the unblinded examiner to the alternate setting (burst DBS in case that the patient first was turned on with their baseline DBS setting or baseline DBS setting in case that the patient was first turned on with burst DBS setting) and kept on this setting for 30 minutes.
- After 30 minutes, the blinded examiner will perform another UPDRS-III evaluation. Patients, who are blinded to the stimulation setting, will be asked if they preferred one stimulation mode over the other.
- If any adverse events occur with burst DBS mode, the unblinded examiner will decrease the amplitude of the DBS by 0.5mA increments until the adverse events abate. If there are not persistent adverse events with 30 minutes of burst DBS mode, the patient will be kept in burst DBS mode at the end of first visit and will be allowed to take their Parkinson's disease medications.

Figure 1. Visit 1 Assessment Schema

Randomization Procedure

Subjects will be randomized to determine which DBS setting is initially programmed during visit one. All subjects will be programmed to both settings over the course of the visit, but the order is randomized to ensure appropriate blinding of the UPDRS assessor. Subjects have a 50% chance of being randomized to the “burst” mode, and a 50% chance of being randomized to the “baseline” mode. Following the initial UPDRS assessment (Meds OFF/DBS OFF), the study coordinator or unblinded assessor will use a computerized randomization system to determine which DBS setting the subject receives first.

Visit Two (6 months +/- 30 Days)

- Parkinson’s disease dopaminergic medications will be withdrawn overnight to establish medication-OFF state and DBS will be turned OFF overnight for establishing DBS-OFF state.
- Examiner will establish a UPDRS-III baseline with medication-OFF, DBS-OFF state. Examiner will then turn the DBS ON to the burst DBS state and keep ON for 30 minutes. After 30 minutes the examiner will perform another UPDRS-III evaluation and will ask about any adverse effects. Patients will then be allowed to take their Parkinson’s disease medications and will be kept on the burst mode DBS state.
- Patients will be asked if they prefer the burst mode DBS state to their baseline settings before the study.

Visit Three (12 months +/- 30 days)

- Parkinson’s disease dopaminergic medications will be withdrawn overnight to establish medication-OFF state and DBS will be turned OFF overnight for establishing DBS-OFF state.
- Examiner will establish a UPDRS-III baseline with medication-OFF, DBS-OFF state. Examiner will then turn the DBS ON to the burst DBS state and keep ON for 30 minutes. After 30 minutes the examiner will perform another UPDRS-III evaluation and will ask about any adverse effects. Patients will then be allowed to take their Parkinson’s disease medications and will be kept on the burst mode DBS state.
- Patients will be asked if they prefer the burst mode DBS state to their baseline settings before the study. At the conclusion of the study, patients will be asked if they want to continue to use burst DBS state or if would prefer to be programmed back to their pre-study baseline DBS settings.

Phone Follow-Up Visits

Phone follow up calls will be completed by study personnel to determine subject’s programming preference at 1 week, 1, 3 and 9 months post programming changes.

Table 1. Schedule of Study Events

Activities	Screening/ Enrollment	Visit 1 (Baseline)	Visit 2 Month 6 +/- 30 days	Visit 3 Month 12 +/- 30 days	Phone Follow-up ⁴
Informed Consent	x				
Demographics	x				
Medical History	x				
Parkinson's Medications	x	x	x	x	x
Concomitant medications	x	x	x	x	x
Adverse Events		x	x	x	x
Serious Adverse Events		x	x	x	x
Adverse Device Effects		x	x	x	
UPDRS III (Meds OFF ¹ /DBS OFF ²)		x	x	x	
UPDRS III (Meds OFF ¹ /DBS ON- Burst)		x	x	x	
UPDRS III (Meds OFF ¹ /DBS ON- Baseline ³)		x			

¹ Parkinson's disease dopaminergic medications should be withdrawn overnight to establish medication-OFF state

² DBS should be turned off overnight to establish DBS-OFF state

³ DBS should be programmed to the baseline settings patient had before study entry

⁴ Phone follow up calls to determine subject's programming preference will be completed by study personnel at 1 week, 1, 3 and 9 months post programming changes.

DBS Programming Procedure

Each time that programming is performed it will be conducted in the same manner as is done for DBS in movement disorders: each electrode will be systematically checked for impedance. The optimal electrodes will be used in either monopolar or bipolar mode to maximize the clinical benefit. At no time will charge densities above 30 microCoulombs/cm² /phase be applied.

The parameters that may be are, the polarity of stimulation (off, negative, or positive), bipolar or monopolar stimulation, the amplitude (0-0.1 mA), the pulse width (10-450 msec), and the frequency of stimulation (2-225 Hz). Each programming session will be performed in the same manner: Beginning on the right side of the body, interrogate the stimulator with the Access Review device. Determine if the device has been on continuously since the last visit, and if there were any activations. The impedance of that device will then be measured (normal impedance 250–2,000 OHMs). In this protocol, subjects will be blinded to which electrodes will be active during each test period of stimulation.

Outcomes Being Measured

Adverse Events and Serious Adverse Events

An adverse event (AE) is any undesirable experience (sign, symptom, illness, or other medical event) occurring in the patient, regardless if it is associated with the investigational procedure that appears or worsens during the clinical study.

A serious adverse event (SAE) is one that:

- Results in death
- Is life-threatening
- Requires inpatient hospitalization or prolongs hospitalization
- Result in disability or permanent damage to the body's function or structure
- Results in a congenital anomaly or birth defect
- Required intervention to prevent permanent impairment or damage
- Or, is an important medical event - when the event does not fit the other outcomes, but may jeopardize the patient and may require medical or surgical intervention (treatment) to prevent one of the other outcomes.

Adverse event information will be collected throughout the study, beginning once the patient is enrolled in the study and monitored until each event is adequately resolved or explained. An AE or SAE description (including the nature of the event, date and time of onset, determination of non-serious versus serious, intensity, duration, causality, and outcome of the event) will be recorded on the case report forms by the investigator or research coordinator. A summary report of all serious adverse events will be provided to the reviewing IRB annually. Serious adverse events will be reported within 5 days of the investigator learning of the event to the reviewing IRB.

Secondary Endpoints

Burst DBS may require less energy and therefore a secondary endpoint we will include is a calculation of IPG (implanted pulse generator) or battery longevity. Secondary endpoints will also patient preference for stimulation mode.

Statistical Methods

Statistics will be performed using Mann-Whitney-U test and p-value < 0.05 will be required for statistical significance.

Regulatory and Ethical Considerations

Compliance Statement

This study will be conducted in full accordance all applicable Allegheny Health Network Research Policies and Procedures and all applicable Federal and state laws and regulations including 45 CFR 46, 21 CFR Parts 50, 54, 56, 312, 314 and 812 and the Good Clinical Practice: Consolidated Guideline approved by the International Conference on Harmonisation (ICH). All episodes of noncompliance will be documented.

The investigators will perform the study in accordance with this protocol, will obtain consent and assent, and will report unanticipated problems involving risks to subjects or others in accordance with the AHN IRB Policies IRB Policies and Procedures and all federal requirements. Collection, recording, and reporting of data will be accurate and will ensure the privacy, health, and welfare of research subjects during and after the study.

Risk Assessment

Risks of the study are minimal. Patients may experience a temporary worsening of motor symptoms when they stop medications the night before patient visits and may also experience a temporary worsening of motor symptoms when programmed into burst-type DBS. These motor symptom changes, if they do occur, would be reversible, and no patient will be required to continue using burst-type DBS after the first visit if they do not want to or if they find the motor symptom changes worse or bothersome. Patients may contact a member of the study team if they wish to exit the study or stop using burst-type DBS programming at any time.

Potential Benefits of Participation

The potential benefits of burst-type DBS include the potential of better motor symptom control including improved tremor, improved rigidity, and improved dyskinesias. An additional benefit may be that burst-type DBS may require lower energy for treatment and could therefore prolong DBS implanted pulse generator (IPG) life.

Confidentiality

All data and records generated during this study will be kept confidential in accordance with Institutional policies and HIPAA on subject privacy and that the Investigator and other site personnel will not use such data and records for any purpose other than conducting the study. All patient data will be de-identified and kept on a secure computer within the Neuroscience Research Department at Allegheny General Hospital.

No identifiable data will be used for future study without first obtaining IRB approval. The investigator will obtain a data use agreement between the provider (the PI) of the data and

any recipient researchers (including others at AHN) before sharing a limited dataset (PHI limited to dates and zip codes).

Data Safety Monitoring

The research team, including the PI, will meet a minimum of every 12 months to review accruals, adverse events, potential breaches in confidentiality and any unanticipated problems related to this research. Any identified reportable events or breaches in confidentiality will be reported immediately to AHNRI IRB and AHN Privacy Department. Any events or changes in the risk/benefit ratio affecting decisions about study continuation will be submitted to the IRB immediately via a prompt report form.

Payment to Subjects

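### Three primary time points share one unadjusted p < 0.05 with no deciding contrast, so the primary claim could rest on a 6- or 12-month result that lacks the controls of Visit 1

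*Combined protocol and SAP*

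**What the plan says.** The Primary Objective section of the combined protocol and SAP asks for change in UPDRS-III "in the acute setting (after 30 minutes) and then after 6 months and 12 months". It does not say what the change is measured from.

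The Statistical Methods section is one sentence: "Statistics will be performed using Mann-Whitney-U test", and "p-value < 0.05 will be required for statistical significance". It gives no deciding time point, testing order, alpha split or requirement that all time points succeed. It does not state sidedness or say which comparisons the threshold governs.

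The Study Design section describes a "Randomized, double-blind cross-over study with N= 5 patients". Withdrawn patients may be replaced "to ensure the number of completed subjects equals 5".

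On the assessments, the Randomization Procedure section says of Visit 1: "All subjects will be programmed to both settings over the course of the visit". Visit One specifies a blinded examiner who did not do the programming. For Visits Two and Three the text reads: "Examiner will then turn the DBS ON to the burst DBS state and keep ON for 30 minutes". The examiner then scores UPDRS-III again. Table 1 schedules the usual-setting score at Visit 1 only.

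**The concern.** Because no rule ranks the three time points, the natural reading is that any one p < 0.05 meets the stated criterion. The text does not say this outright, but it offers nothing else.

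The three time points are not equal evidence. The 30-minute comparison is the crossover that the Study Design section advertises. The 6- and 12-month results are burst scores with only a same-visit DBS-OFF score beside them. A primary claim could therefore come from the weaker part of the study while carrying the description of the stronger part. The undefined reference adds a further choice, since burst could be compared with same-visit DBS-OFF or with the Visit 1 usual setting.

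The second matter is the error rate. With three chances to succeed, the stated 0.05 need not be the chance of a false primary claim.

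**Working it through.** **Inputs from the documents.** Three primary time points (Primary Objective); threshold 0.05 and Mann-Whitney U (Statistical Methods); five patients, each measured under every condition (Study Design, Randomization Procedure). The plan gives no familywise error, power or sample-size figure, so there is none to reproduce.

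**Assumptions.** Tests are two-sided. Correlations are not given, so ranges are shown. Simulations use normal scores with no true differences.

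**1. What each time point offers**

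| | 30 min (Visit 1) | 6 months | 12 months |
|---|---|---|---|
| Randomised order | yes | no | no |
| Blinded examiner specified | yes | no | no |
| Usual-setting score at same visit | yes | no | no |
| DBS-OFF score at same visit | yes | yes | yes |

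**2. Planned Mann-Whitney, 5 v 5.** There are C(10,5) = 252 arrangements. Two-sided rejection at U ≤ 2 or U ≥ 23 has probability 8/252 = 0.0317. Adding U = 3 and its mirror image gives 0.0556, which is too large. Three independent tests give 1 − (1 − 0.0317)³ = 0.092.

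The scores come from the same five patients, so independence is unlikely. Simulated familywise error on raw scores:

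| Within-patient correlation | Against same-visit score | Against shared Visit 1 score |
|---|---|---|
| 0 | 9.3% | about 8% |
| 0.3 | 4.6% | 4.2% |
| 0.5 | 2.4% | 2.3% |
| 0.7 | 0.9% | 0.8% |
| 0.9 | 0.1% | 0.1% |

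Suppose instead that each burst change from its own DBS-OFF score is compared with the Visit 1 usual-setting change from DBS-OFF. The familywise error is then about 6.5% at every correlation from 0 to 0.9, because the patient effect cancels. The Visit 1 test contributes about 0.8%, as both its changes share one OFF score. The 6- and 12-month tests contribute about 3.2% each.

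**3. Three paired t tests, n = 5.** If independent: 1 − 0.95³ = 0.143. Simulated, by correlation between the three change scores:

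| Correlation | 0 | 0.3 | 0.5 | 0.7 | 0.8 | 0.9 |
|---|---|---|---|---|---|---|
| Familywise error | 14.3% | 13.9% | 13.2% | 12.0% | 10.9% | 9.4% |

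**4. Exact signed-rank test, n = 5.** There are 2⁵ = 32 sign patterns. The smallest two-sided p is 2/32 = 0.0625, above 0.05. The test can never reject, so familywise error and power are both 0%.

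**5. One paired t test at 0.05, n = 5.** The error is 5% if the differences are normal. A power of 80% needs a mean difference of about 1.7 standard deviations of the within-patient differences.

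**The case against.** The strongest reply is that the planned analysis is conservative on raw scores. At a within-patient correlation of about 0.3 or more, the Mann-Whitney familywise error is under 5%. A reader might infer from three tests at 0.05 that the plan's false-positive rate is 13–14%. The documents do not support that. The figure needs paired t tests, which they never mention, and a correlation between change scores of about 0.5 or less. Nor does it follow from using just any paired test, since the exact two-sided signed-rank test gives 0%. This part of the objection stands.

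A reader might also count every pair among a patient's UPDRS-III scores, or every contact at which preference is asked, as further inflation. That does not hold either. Many of those pairs, such as DBS-OFF at one visit against DBS-OFF at another, do not address change with burst stimulation, and preference is a secondary endpoint.

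It can also be said that multiplicity ranks behind other defects in a five-patient study: an unpaired test on paired data, an undefined reference for change, and very low power. That is fair, and the fix has to deal with these together.

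What the objection does not remove is the missing deciding contrast. The conservatism comes from applying an independent-samples test to crossover data, and it goes once a paired t test replaces that test. It also does not cover change-from-OFF scores, where the figure is about 6.5%. The possibility of a primary claim on an uncontrolled late result exists whatever the error rate.

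**Conclusion.** The point holds as a gap in what decides the trial, and as a modest, test-dependent concern about error. The first part rests on the text alone: three time points, one threshold, no order, no reference for change, and only Visit 1 with randomised order, a specified blinded rater and a usual-setting score. The documents do not say that the later examiner is unblinded; they simply do not specify blinding there.

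The second part has no single number. The range runs from 0% (exact two-sided signed-rank) to about 14% (paired t tests with low correlation), with the planned Mann-Whitney between about 0.1% and 9% according to the correlation and the scores compared. All of these assume two-sided testing and rest on correlations that the documents do not supply. The change is worth making because it is cheap and protects the meaning of the primary result, not because the plan as written has a demonstrated 13–14% error rate.

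**What to change.** In Primary Objective, name one primary contrast: the within-patient difference in medication-OFF UPDRS-III between burst and the usual setting at Visit 1, 30 minutes after each setting is switched on.

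In Statistical Methods, replace the Mann-Whitney for this contrast with a paired test that can reach 0.05 with five patients, for example a two-sided paired t test with its 95% interval. The exact two-sided signed-rank test cannot. State the reference for change at months 6 and 12 (same-visit DBS-OFF is the only concurrent score), and report those results as estimates with intervals and no significance claim.

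The cost is about two sentences and no new data. Two downsides should be accepted openly. An isolated 6- or 12-month p-value can no longer be claimed as a primary result. The paired t test also relies on roughly normal differences, which five patients cannot verify, and it has good power only for very large effects.

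### The Visit 1 crossover draws the order of settings with no stated balance, and the analysis does not use the recorded order, so a period effect could stay in the estimate from 5 patients

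*Combined protocol and SAP*

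**What the plan says.** All places are in the combined protocol and SAP.

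- **Before the first setting** (Visit One – Baseline): "DBS will be turned OFF overnight for establishing DBS-OFF state". A UPDRS-III is taken in that state, the first setting runs for 30 minutes, and a blinded examiner scores it.
- **Before the second setting** (same section): "Next, the DBS will be turned off for 15 minutes to permit for a washout period". The alternate setting then runs for 30 minutes and is scored.
- **OFF scores.** The text and Table 1 list no DBS-OFF score after the washout. Table 1 has one DBS-OFF row, with the footnote "DBS should be turned off overnight to establish DBS-OFF state". The drawing under "Figure 1. Visit 1 Assessment Schema" could not be read in the copy reviewed, so a score shown only there cannot be excluded.
- **Where the settings are compared.** Table 1 schedules the baseline-setting score at Visit 1 only.
- **Order** (Randomization Procedure): "Subjects have a 50% chance of being randomized to the" burst mode, and the same chance of the baseline mode, drawn by a computerized system that is not described further. The reason given is that "the order is randomized to ensure appropriate blinding of the UPDRS assessor". No block, fixed split or rule for a replacement patient's order is stated.
- **Numbers.** Recruitment Strategy expects about 15 enrolled to yield 5 evaluable patients. Subject Replacement allows replacement until 5 complete.
- **Analysis** (Statistical Methods): one sentence naming the Mann-Whitney U test at p < 0.05. It names no contrast, within-patient difference, period or sequence.
- **Data** (Appendix A, Visit 1 form): the unblinded examiner records which setting came first.

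**The concern.** The two periods do not start alike. The second score comes after a much shorter DBS-OFF interval, later in medication-OFF, and after one more examination. Anything that moves the score between the first and second ON assessment, whatever the setting, is a period effect. In a crossover it cancels from the treatment difference only if the two orders are equally frequent or the analysis allows for order. Five patients cannot split evenly, no balance is stated, and the analysis names no allowance.

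A second route is unequal carryover. The opening section cites animal work: "Recent animal studies of DBS suggest that neuronal subpopulations may be specifically activated by burst-type DBS", and "this type of electrical stimulation programming may improve the efficacy and durability of DBS". If burst leaves the longer residual effect, baseline settings would look better when they come second. No size is given, and balancing the order does not remove this.

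At stake is the only within-study evidence on whether burst differs from the patient's own settings on the motor score. In patients who receive baseline first, the acute burst score used for the primary objective is also a post-washout score.

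**Working it through.** The plan gives no effect size, SD, power or period effect, so there is no plan figure to reproduce.

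**Inputs from the protocol:** 5 completers; 50% chance of each order; 15 minutes off plus 30 minutes on the second setting; about 15 enrolled. **Assumed:** independent draws; sizes of the period effect; block sizes 2 and 4; completion unrelated to order.

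**1. Time between ON scores.** 15 + 30 = at least 45 minutes.

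**2. Order split.** Binomial(5, 0.5):
- 3:2 = 20/32 = 62.5%
- 4:1 = 10/32 = 31.25%
- 5:0 = 2/32 = 6.25%
- 4:1 or 5:0 = 12/32 = 37.5%

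**3. Share of a period effect left in the mean paired difference.** Let P be the period effect (second minus first) and k the number who receive burst first. The mean burst-minus-baseline difference contains P(5 − 2k)/5, so the share is |n1 − n2|/5.

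| Split | Share | P = 1 point | P = 3 | P = 5 |
|---|---|---|---|---|
| 3:2 | 20% | 0.2 | 0.6 | 1.0 |
| 4:1 | 60% | 0.6 | 1.8 | 3.0 |
| 5:0 | 100% | 1.0 | 3.0 | 5.0 |

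The sign depends on which order is in excess, and the average over random orders is zero.

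**4. Averaging the two sequence means.** One sequence mean contains +P and the other −P, so P cancels at any split except 5:0, where one sequence is empty. With residual effects Cburst and Cbase, the burst benefit is shifted by (Cbase − Cburst)/2 at any split. For an assumed excess of burst over baseline residual of 0, 1, 2 or 4 points, the shift against burst is 0, 0.5, 1.0 or 2.0 points. Averaging does not remove it.

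**5. Precision cost with no period effect.** Variance ratio to the simple paired mean = (1/4)(1/n1 + 1/n2)/(1/5), which is 1.042 at 3:2 and 1.5625 at 4:1. One degree of freedom is lost (t = 3.182 on 3 df, against 2.776 on 4).
- 3:2: √1.042 × 3.182/2.776 = 1.17, or 17% wider
- 4:1: √1.5625 × 3.182/2.776 = 1.43, or 43% wider

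A period effect also inflates the expected variance of the simple paired differences, by 1.2P² at 3:2 and 0.8P² at 4:1. The two intervals are equally wide at P = √((1.170² − 1)/1.2) = 0.55 SD of the within-patient differences (3:2) and √((1.433² − 1)/0.8) = 1.15 SD (4:1).

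**6. First-period-only comparison at 3:2.** Half-width of the 95% CI = 3.182 × √(1/3 + 1/2) = 2.91 SD of the first-period change. This supports a listing, not an estimate.

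**7. What a blocked list achieves.** Suppose N are randomised until 5 complete: the Nth completes, and the other 4 completers are a random subset of the first N − 1. Example with blocks of 2 and N = 15: the first 14 entries are 7:7, and 4 of 14 can be chosen in 1,001 ways. Of these, 35 + 245 + 35 = 315 give 4:1 or 5:0, so 315/1,001 = 31%.

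| N randomised | P(4:1 or 5:0), blocks of 2 | Blocks of 4 |
|---|---|---|
| 5 | 0% | 0% |
| 6 | 0% | 13% |
| 8 | 14% | 14% |
| 10 | 21% | 26% |
| 15 | 31% | 29% |

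The largest P(5:0) is 3.5%, against 6.25% for independent draws.

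**8. False positives.** Mann-Whitney U was simulated with no true difference and a 5-point period effect, at assumed between- and within-patient SDs of 10 and 4. It rejected in 0.2% of trials averaged over random order and 1.4% at 5:0. With SDs of 5 and 3 the rates were 1.1% and 10%.

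**The case against.** The plan already has safeguards: random order, a washout, patient blinding, a blinded examiner for the Visit 1 ON scores, and a form that records the order. Because the second score follows 30 minutes of the alternate stimulation, any residual effect must last at least 45 minutes, not 15. The harm is also measured on a mean paired difference that the plan never names. Its larger gap is that no contrast is defined at all. The stated primary objective is change with burst, not burst against baseline. The remedy is modest: blocking gains little if about 15 are randomised, and the averaged estimate rests on 3 degrees of freedom.

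Most of this stands, and it limits the weight of the point. It does not answer it, because any report of burst against baseline must use these five pairs of scores.

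A reader might infer three stronger things that the documents do not support:
- **That order will be unbalanced.** The system is not described, and it may block.
- **That Visit 1 is biased against burst.** This needs unequal carryover, and the only support is an animal-study suggestion without a size.
- **That the planned test will give false positives.** Averaged over random order, its simulated error rate stayed well below 5%. It exceeded 5% only in an extreme case: a 5:0 split, a 5-point period effect and the smaller assumed SDs.

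**Conclusion.** The point holds as a cheap improvement to the plan, not as a defect that invalidates Visit 1. If draws are independent, there is a 37.5% chance that at least 60% of any period effect stays in the mean burst-minus-baseline difference, including a 6.25% chance that setting and period are fully confounded. Even the best split, 3:2, keeps 20%. These shares are exact. The point values are not findings, because the documents give no period effect, carryover effect or SD. The expected bias from a period effect is zero under random order; the concern is the one split that occurs. Visits 2 and 3 score burst only, after overnight DBS-OFF, and are not affected. If the computerized system already balances order, saying so settles that part. The unused order information in the analysis remains.

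**What to change.** 1. **Allocation.** Draw order from a concealed, pre-generated permuted-block list. Do not disclose the block size to site staff, and release each entry only after the overnight-OFF score. A replacement takes the next entry on the list. Reusing the withdrawn patient's order would hold a planned split, but staff who know that order would know the replacement's in advance. The gain is large if few patients are replaced and small if about 15 are randomised (29 to 31% against 37.5%).
2. **Reporting.** List all Visit 1 scores by sequence and period for every randomised patient, including those later replaced. Report the average of the two sequence-specific mean within-patient differences with a 95% CI, labelled descriptive. State that it removes a period effect but not unequal carryover, and that it cannot be computed at 5:0. Show the first-period changes from the overnight-OFF score as a listing; these carry nothing over from the other Visit 1 setting.

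Cost: one list and some analysis wording, with no new visit, patient or measurement. Staff who know earlier orders could still guess some entries in small blocks. With no period effect, the interval is about 17% wider at 3:2 and 43% wider at 4:1 than for the simple paired mean. No extra assessment is requested and no washout length is proposed.
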